- C. By accessing the cranial nerves in the manner described above, the effect may be cumulative and residual and offer the patient immediate, intermediate and longer lasting results and relief.

For the reasons cited above, Nu-Life will be submitting Nu-V3 for FDA clearance under De Novo 513(f)(2), as a new and unique technology. In part, the purpose of this clinical study is to demonstrate the effect upon the four specific symptoms of pain, anxiety, depression and sleeplessness, as any one or combination of these symptoms may result in Autonomic Nervous System dysfunction.

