## 4.0 STUDY PROTOCOL

The Nu-V3 Clinical Study is a prospective, single-arm, open-label, multi-center study using the Nu-V3 cranial nerve stimulation treatment device in patients with pain, anxiety, depression, and/or sleeplessness.

For this Phase I study, a total of 50-100 patients at multiple centers will be registered for study participation. Study participants are those who have signed the informed consent form, met the inclusion and exclusion criteria, and are enrolled in the study at one of multiple sites. Enrolled participants are stratified based on their pain, anxiety, depression, and/or sleeplessness symptom presentation at baseline and treated with the Nu-V3 device for 8 weeks, then observed for an additional 4 weeks. Interim analysis of reported data will be based on baseline stratifications and conducted at 4, 8, and 12 weeks during this time. Post study, participants will be given the chance to continue with an optional maintenance treatment with the Nu-V3 device per a 2-weeks on, 2-weeks off schedule, for an additional 12 weeks, with an 8-week observation.

Subjects enrolled onto the Nu-V3 Clinical Trial will undergo the following regimen:

- At the baseline visit, patients will be asked to complete study questionnaires (Appendix 11) regarding all of the following symptoms: pain, anxiety, depression, and/or sleeplessness, as well as their quality of life, active medications, medical history, and demographical information.
- At each subsequent visit, patients will be asked to complete study questionnaires regarding all the following symptoms: pain, anxiety, depression, and/or sleeplessness, as well as their activity level and quality of life.
- The sessions will begin with the Nu-V3 device being placed on the left ear and three small pads (non-invasive) being placed on the ear. Each Nu-V3 device

lasts for up to 14 days with a change in the pads approximately 7 days into the treatment.

- Each session takes approximately 15-20 minutes. The placement of the device takes approximately 5 minutes and the remaining time is spent verifying ePRO form completion, and evaluating the patient for all device effects.
- The Nu-V3 device is mobile and is worn externally on the left ear 24 hours a day during treatment, fitting comfortably behind the ear. An electrical signal is sent to the external ear through coated wire leads attached to the device and adhesive pads which attach to three sites on the ear.

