## 5.0 DATA COLLECTION AND RETENTION

The study endpoints data will be collected from each participant's study questionnaires. The data will be collected electronically via the patient's own device, and uploaded to an electronic data capture system. Only patient data from the stratified indication(s) will be used for analysis of symptom response. The data will be used to demonstrate that the Nu-V3 device provides participants with relief of the symptoms of pain, depression, anxiety and/or sleeplessness. The data analysis will include comparative data for each participant's questionnaire prior to beginning treatment with the Nu-V3 device, the participant's weekly questionnaires during

treatment and the questionnaire completed at the end of the treatment with the Nu-V3 device.

Interim analyses of available data will be regularly submitted to the FDA for review.

The Principal Investigator at each site will be responsible for recording, collecting, and storing the research participant's study data. The written records must be stored in a secure location. Only the Principal Investigator or designated study staff will have access to the study records and all electronic files will be password protected. The Principal Investigator will also maintain adequate records for the study including:

- all correspondence with the IRB and Sponsor
- other pertinent data related to the study

All records are to be retained by the Principal Investigator for a period of seven (7) years following the closure of the study. Following study closure, the Principal Investigator shall inform Nu-Life of the location of study records and storage changes (i.e. the Principal Investigator leaves the institution where the study was conducted). In such cases, the study records may be transferred to another institution, investigator, or to Nu-Life upon written agreement between the Principal Investigator and Nu-Life.

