### 8.2 Secondary Endpoints: Secondary endpoints consisted of the following:

Effectiveness: The secondary effectiveness endpoint is an overall change in median reported symptoms of pain, anxiety, depression, and/or sleeplessness for respective stratified populations via numeric rating scales at 4, 8, and 12 weeks. This is measured via the following validated tools: Pain – Pain Intensity and Interference (PEG\_Scale), Anxiety - Generalized Anxiety Disorder 7-item (GAD-7) scale, Depression - Patient Health Questionnaire (PHQ-9), Sleeplessness - PROMIS short form 4a, and overall improvement of quality of life- Patient’s Global Impression of Change (PGIC).

The patient’s perceived treatment benefit and device comfort information will be captured via the non-validated tool, Perceived Treatment Benefit Form (PTB-7). This effectiveness tool will measure median levels of reported perceived treatment benefit and device comfort.

The hypothesis-driven criterion is to show that there is a statistically significant reduction in the median reported pain, anxiety, depression, and/or sleeplessness levels of patients using the Nu-V3 device at weeks 4, 8, and 12. The second criterion is intended to show that there is a statistically significant improvement in reported quality of life and perceived treatment benefit secondary to overall reported symptom reduction of pain, anxiety, depression, and/or sleeplessness at weeks 4, 8, and 12.

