### 8.3 Sub-Analyses: Sub-Analyses Consist of the following:

The sub-analyses endpoints consist of the mean number of weeks that pain, anxiety, depression, and sleeplessness response are achieved and sustained, without utilization of another device, during the 8-week intervention. In addition, study sub-analyses also include the mean number of weeks to initial benefit from Nu-V3 device use, and the mean medication dosage reduction of short acting pain, anxiolytics, and/or insomnia. The device's comfort-of-use, and patient's perceived treatment benefit will also be captured for sub-analyses.

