Unique Protocol ID: Nu-V3 Phase I

NCT Number: (not yet assigned)

Brief Title: Nu-V3 Non-Invasive Nerve Stimulation Device Trial for Pain, Anxiety, Depression, Sleeplessness

Official Title: A Phase I Prospective, Single-Arm, Open-Label, Multi-Center Study Using the Nu-V3 Cranial Nerve Stimulation Treatment Device in Patients With Pain, Anxiety, Depression, and/or Sleeplessness

INVESTIGATIONAL DEVICE: Nu-V3

SPONSOR: Nu-Life Solutions

Phase I & II Statistical Analysis Plan*

**All initial graphs and table data are simulated and will be
φ updated at time of study submission

VERSION DATE: 03/APR/2018

Summary of Clinical Information

The primary pivotal study provided to support the De Novo request is the “Nu-V3 Protocol No. 1”- phases I & II. Details of the study design and selected clinical results are provided below.

Purpose: The objective of this research study was to collect data which demonstrates the ability of the Nu-V3 device to offer relief from one or more of the following symptoms: pain, depression, anxiety, and/or sleeplessness. The objective is to demonstrate the effectiveness of Nu-V3 for any or all of the four symptoms listed.

Design: The Nu-V3 Clinical Study was a prospective, single-arm, open-label, multi-center, global study using the Nu-V3 cranial nerve stimulation treatment device in patients with uncontrolled pain, anxiety, depression, and/or sleeplessness. For the Phase I study, a total of _____ patients at _____ centers in the United States were registered for study participation. A total of _____ patients at _____ centers in the United States, Japan, India, Germany, United Kingdom, Austria, Switzerland, _____, were registered to the Phase II study.

Phase I study consisted of 50-100 individuals who signed the informed consent form, met the inclusion and exclusion criteria, and were enrolled in the study at multiple sites. Enrolled participants are treated with the Nu-V3 device for 8 weeks, then observed for an additional 2 weeks. Interim analysis of reported data were conducted at 4, 8, and 12 weeks during this time. Post study, participants were given the chance to continue with an optional maintenance treatment with the Nu-V3 device per a 2-week on, 2-week off schedule, for an additional 12 weeks, with an 8-week observation.

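### The secondary hypothesis treats Week 12 as an on-device time point although the schedule has the device off from Week 9, and no post-removal comparison is prespecified

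*Protocol*

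**What the plan says.** **Hypothesis.** Protocol section 8.2 aims to show a significant reduction in median pain, anxiety, depression and/or sleeplessness "levels of patients using the Nu-V3 device at weeks 4, 8, and 12". The SAP's Secondary Endpoints paragraph uses the same words.

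**Device schedule.** Protocol section 4.0 has participants "treated with the Nu-V3 device for 8 weeks, then observed for an additional 4 weeks". The assessment tables in protocol section 4.1 and in the SAP agree with that: the last new device is placed in Week 7, the last pads are changed in Week 8, and the row for no device is marked for Weeks 9-11 and Week 12. The SAP's Design paragraphs, for both phases, say instead that participants are "then observed for an additional 2 weeks", while still planning an analysis at 12 weeks.

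**Comparisons named.** Protocol section 5.0 lists the "questionnaire prior to beginning treatment with the Nu-V3 device", the weekly questionnaires during treatment, and "the questionnaire completed at the end of the treatment with the Nu-V3 device". The SAP's Study Endpoints and Data Analysis paragraph lists the same three. Section 8.3 counts sustained response "without utilization of another device, during the 8-week intervention". The secondary-endpoint entry in the SAP's Results section is a placeholder for a table at 4, 8 and 12 weeks.

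**Rationale.** Protocol section 1.1, item C, says that "the effect may be cumulative and residual and offer the patient immediate, intermediate and longer lasting results and relief".

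**The concern.** The secondary hypothesis groups two on-device time points with one off-device time point and describes all three as results in device users. Weeks 4 and 8 ask whether symptoms are lower while the device is worn. Week 12 asks whether anything remains after removal. If Week 12 is read against baseline, a significant reduction cannot distinguish an effect that was kept from one that has mostly worn off.

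The comparison that would speak to the residual-effect rationale is end of treatment against a later off-device score, and it appears nowhere. Questionnaires are scheduled in Weeks 9 to 12, but the analysis text names only data up to the end of treatment. The SAP presents this work as the pivotal evidence for a De Novo request, so wording that describes off-device results as results in device users could carry over into the effectiveness statement.

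**Working it through.** The documents give no alpha, SD, effect size or power calculation for this endpoint, so there is no stated figure to reproduce.

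**1. Is Week 12 wholly off the device?** Take the Week 1 visit as day 0 (my reading of the table).
- The last device goes on in Week 7, day 6 × 7 = 42. It lasts up to 14 days, so treatment ends about day 56.
- The Week 12 visit is day 11 × 7 = 77. Gap: 77 − 56 = 21 days.
- With the ±3-day window used against us at both ends: (77 − 3) − (56 + 3) = 15 days.
- Recall periods in Appendix 11: one week for PEG and PROMIS 4a, two weeks for GAD-7 and PHQ-9. The smallest gap, 15 days, exceeds the longest recall, 14 days.

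All four Week 12 symptom scores therefore describe off-device time only. Weeks 9 to 11 are less clean. The Week 10 visit (day 63) has a two-week recall reaching back to day 49, a week before treatment ends.

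**2. How small a residual is significant against baseline?** Assumptions: two-sided alpha 0.05; a 3-point PEG fall at Week 8; SD of the baseline-to-Week-12 change 2.5, range 2 to 3; a paired t-test standing in for the unspecified test of medians. The smallest significant observed change is t(0.975, n−1) × SD/√n, and the loss is 1 − change/3.

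| n | SD 2 | SD 2.5 | SD 3 |
|---|---|---|---|
| 25 | 0.83 (72% lost) | 1.03 (66%) | 1.24 (59%) |
| 50 | 0.57 (81%) | 0.71 (76%) | 0.85 (72%) |
| 100 | 0.40 (87%) | 0.50 (83%) | 0.60 (80%) |

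Example at n=50 and SD 2.5: 2.010 × 2.5/√50 = 0.71, and 1 − 0.71/3 = 0.76. A 1-point residual there gives t = 1/(2.5/√50) = 2.83 and p = 0.007, with two thirds of the gain lost.

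The protocol's 50-100 is the whole trial. Each scale is analysed in its own symptom stratum, so n=25 is included as a possible stratum size.

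**3. How likely is it?** The table gives cutoffs for an observed change, not probabilities. Power from the noncentral t is 1 − F(t(0.975, n−1); n−1, d√n). Assume a standardized Week 8 change of 0.8 with 60% lost, so d = 0.8 × 0.4 = 0.32 at Week 12. For the paired Week 8-to-12 change, d = 0.8 × 0.6 = 0.48, taking the SD of that difference as equal to the SD of change (a correlation of 0.5 between the two changes).

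| n | Week 12 significant against baseline | Loss detected by the paired Week 8-to-12 change |
|---|---|---|
| 25 | 0.34 | 0.63 |
| 50 | 0.60 | 0.91 |
| 100 | 0.89 | 0.997 |

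A simulated Wilcoxon signed-rank test gives 0.59 and 0.87 for the middle column at n=50 and n=100. Over Week 8 effects of 0.5 to 1.0, losses of 60-80% and n of 25 to 100, the chance of a significant Week 12 result runs from 0.07 to 0.98.

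**4. SAP timing.** 8 + 2 = 10 weeks, which stops short of the SAP's own Week 12 analysis. The protocol's 8 + 4 = 12 reaches it.

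**The case against.** The best defence is that the phrase about patients using the device merely names the treated population. Section 8.1 uses it with no time point, and section 4.0 and both tables state device status openly. On that reading this is loose drafting on a secondary endpoint. A table of results at 4, 8 and 12 weeks would also put the medians side by side, where a large loss would be visible. Both points stand as mitigation. They do not supply a prespecified comparison, and section 8.2 attaches the phrase to Week 12 explicitly.

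A reader might go further than the documents allow in three ways.
- **That Week 12 is tested only against baseline.** No reference or test is stated. Section 5.0 makes baseline the natural reading, but its list says what the analysis will include and is not worded as exhaustive.
- **That a largely lost effect would be declared a success.** There is no success rule or durability endpoint, and the probability depends heavily on assumed inputs and on stratum size.
- **That removal after Week 8 is the only on/off information planned.** The optional maintenance period cycles two weeks on and two weeks off, with questionnaires. It is optional and post-study, but it is planned.

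The Week 8-to-12 change has limits too. Removal is unblinded and there is one arm, so expectation and time effects remain.

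**Conclusion.** The point holds in a limited form. As written, the Week 12 hypothesis contradicts the schedule in both documents, its reference is unstated, and no post-removal contrast is prespecified. A significant Week 12 reduction could therefore be reported as effectiveness in device users with much of the Week 8 gain gone. Under the assumptions above, that could happen with about 76% lost at n=50 (72-81% over the SD range) and about 66% lost at n=25 and SD 2.5. These are illustrations of what is possible. The documents do not support saying that it will happen, or that a durability claim is planned: item C of section 1.1 says only that "the effect may be cumulative and residual". The Week 8 primary endpoint is measured on the device and is unaffected.

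**What to change.** 1. In protocol section 8.2 and the SAP's Secondary Endpoints paragraphs, restate the hypothesis as on-device at Weeks 4 and 8 and off-device (post-treatment) at Week 12, and name baseline as the reference for each.
2. Prespecify, for each scale within its symptom stratum, the paired Week 8-to-Week 12 change with a confidence interval. Use Weeks 9-11 descriptively, because the two-week recall of GAD-7 and PHQ-9 can overlap device time.
3. State that Week 12 against baseline alone will not be described as an on-device effect or as durability, that any statement on persistence will rest on the estimate and confidence interval of the Week 8-to-12 change, and that a non-significant loss is not evidence of durability.
4. Reconcile the SAP's 2-week observation period with the protocol's 4 weeks and with the Week 12 analysis.

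The cost is wording and one extra analysis per scale on questionnaires already scheduled. A durability statement becomes harder to make, and in a small stratum the interval may be too wide to settle the question.

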### 8.3 Sub-Analyses: Sub-Analyses Consist of the following:

The sub-analyses endpoints consist of the mean number of weeks that pain, anxiety, depression, and sleeplessness response are achieved and sustained, without utilization of another device, during the 8-week intervention. In addition, study sub-analyses also include the mean number of weeks to initial benefit from Nu-V3 device use, and the mean medication dosage reduction of short acting pain, anxiolytics, and/or insomnia. The device's comfort-of-use, and patient's perceived treatment benefit will also be captured for sub-analyses.

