#### 4.1 Phase I Study Assessment Tables

Nu-Life Solutions Miniaturized Wearable Medical Technology - Nu-V3		Study Treatment Assessments Table										Nu-V3
		*Evaluations are completed weekly, every 7 days =3 days										
Evaluation*	Study Treatment											
	Week 1	Week 2	Week 3	Week 4	Week 5	Week 6	Week 7	Week 8	Week 9-11	Week 12		
Informed Consent	x											
Inclusion and Exclusion 	x											
Patient Registration 	x											
Medications Form 	x			x				x		x		
Patient Onboarding and Orientation 	x											
In office assessment	x	x	x	x	x	x	x	x		x		
New Device Placed	x		x		x		x					
Pad Replaced		x		x		x		x				
Treatment Forms 	x	x	x	x	x	x	x	x				
No Device									x	x		
ePRO Questionnaires 	x	x	x	x	x	x	x	x	x	x		
Patients' Global Impression of Change ePRO form (PGIC) 		x	x	x	x	x	x	x		x		
Providers' Global Impression of Change ePRO form (PGIC)		x	x	x	x	x	x	x		x		
Family Global Impression of Change ePRO form (PGIC)		x	x	x	x	x	x	x		x		
Optional Patient Media Testimony	x			x				x		x		

1. Inclusion/Exclusion, Registration, Medications, Treatment forms to be completed by site coordinator via online module.  
 2. Patient Onboarding and Orientation includes introductory demographics form, Nu-V3 patient training video  
 3. ePRO questionnaires completed on patient's mobile device: DQ-9 (baseline), PTB-7, PEG, GAD-7, PHQ-9, PROMIS 4a, PGIC  
 4. If patient consents to media testimony, site will collect via study collection process every 4 weeks.

Evaluation*	Post Study Intervention Assessments Table														
	*Evaluations are completed weekly, every 7 days ±3 days														
	Optional Maintenance Therapy										Long Term Follow Up				
Week 13	Week 14	Week 15-16	Week 17	Week 18	Week 19-20	Week 21	Week 22	Week 23	Week 24	Week 25	Week 26	Week 27-28	Week 29	Weeks 30-31	Week 32
Medications Form 				x			x			x					x
In office assessment	x	x		x	x		x	x							
New Device Placed	x			x			x								
Pad Replaced		x			x			x							
Treatment Forms 	x	x		x	x		x	x							
No Device			x			x			x	x	x	x	x	x	x
ePRO Questionnaires 	x	x		x	x		x	x	x	x		x			x
Patients' Global Impression of Change ePRO form (PGIC) 	x	x		x	x		x	x				X			X
Providers' Global Impression of Change ePRO form (PGIC)		x			x			x				X			X
Family Global Impression of Change ePRO form (PGIC)		x			x			x				X			X
Optional Patient Media Testimony		x			x			x				x			X

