## 4.2 Protocol Deviations

In the event the Nu-V3 device is inadvertently removed or the device comes off, the participant will contact the Principal Investigator. The Principal Investigator will determine the appropriate course of action to be taken.

If the study participant is unable to wear the device on their left ear, the study participant will be allowed to wear the device on their right ear, which will result in a minor study deviation. Left-ear deviations could be due to discomfort, sleep position, pain at the local site, or infection. A lack of significant improvement by the end of week 4, per the Principal Investigator's discretion, can also result in a deviation from left-ear placement.

Device placement should be recorded on the study treatment form within the electronic data capture system.

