**NOTE TO HEALTH CARE PROVIDER**

A significant, favorable change is a score of 5-7  
 No significant change is a 1-4 response.  
 Note, this a dichotomous scale (5-7 = yes; 1-4 = no).  
 A 2-point change is significant from their last reported score.  
 Reference: Hurst H, Bolton J. Assessing the clinical significance of change scores recorded on subjective outcome measures. *Journal of Manipulative Physiological Therapeutics (JMPT)* 2004;27:26-35.

Subject ID \_\_\_\_\_ Date (dd/mmm/yyyy): \_\_\_\_/\_\_\_\_/\_\_\_\_

[figure not shown]

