The hypothesis-driven criterion was to show that there was a statistically significant reduction in the median reported pain, anxiety, depression, and/or sleeplessness levels of patients using the Nu-V3 device at weeks 4, 8, and 12. The second criterion was intended to show that there was a statistically significant improvement in reported quality of life and perceived treatment benefit secondary to overall reported symptom reduction of pain, anxiety, depression, and/or sleeplessness at weeks 4, 8, and 12.

2. **Sub-analyses:** The sub-analyses endpoints consisted of the mean number of weeks that pain, anxiety, depression, and sleeplessness response was achieved and sustained, without utilization of another device, during the 8-week intervention. In addition, study sub-analyses included the mean number of weeks to initial benefit from Nu-V3 device use, and the mean medication dosage reduction of short acting pain, anxiolytics, and/or insomnia. The device’s

comfort-of-use, and patient's perceived treatment benefit were also captured for sub-analyses.

Eligibility Criteria Summary: The study population consisted of both male and female patients, at least 18 years of age.

Key inclusion criteria included the following:

- Participant presents with one or more of the following symptoms: pain, anxiety, depression, and/or sleeplessness
- Participant can commit to follow all protocol study time-points

Key exclusion criteria included the following:

- Participants with a Pacemaker
- Participants with irregular heart rate or a heart rate lower than 60 beats per minute (bradycardia)
- Have had a transplant within the last 2 years
- Have had a heart attack or cardiac bypass surgery within the last 12 months
- History of substance abuse, including prescription drugs, within the last 12 months
- Patients with complaints of dizziness or lightheadedness within the last 3 months
- Women who are pregnant
- Participants with Diabetic Retinopathy
- Current Ear infection
- SBP < 100 and/or DBP < 60
- History of uncontrolled bipolar disorder within the last 12 months
- History of uncontrolled seizures within the last 12 months
- History of Aneurysms
- History of syncope within the last 12 months
- Participants that have had a TIA or stroke within the last 12 months
- Participants with health problems deemed at risk for the study by the Principal Investigator

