Risks to Health: Potential unanticipated problems require prompt reporting to Aspire IRB. These problems potentially place subjects or others at greater risk of physical or psychological harm than was previously recognized, and warrant consideration of substantive changes in the protocol or informed consent process or other action in order to protect the safety, welfare, or rights of participants. Aspire IRB must be notified within 5 calendar days of the event. The completed IRB Unanticipated Problem form (Appendix 3) must be received by Aspire IRB within 10 calendar days of the event. Unanticipated problems are defined as those problems which alter the risks to subjects or others. This includes any study suspensions or holds. This form will be used to report any problem that is unforeseen or involves risk. One form will be used per event or problem.

Table 4.1: Unanticipated Problems Involving Risk to Patients or Others			
	Phase I	Phase II	Total
UPIRTSO 1 (number)			
UPIRTSO 2 (number)			
UPIRTSO 3 (number)			
Overall UPIRTSOs Reported			

Table 4.2: Risk/ Mitigation Measures	
Identified Risk	Mitigation Measures

Insert Safety Analysis Here

Section 5.0: Results

Results: The principal safety and effectiveness results from patients in the Nu-V3 study are provided below. The primary safety analysis was based on all patients registered and included all reported UPIRTSO events. The primary safety endpoint included imputation for missing clinical outcomes data using the logistic regression method. The imputation model included baseline characteristics including age, sex/gender, marital status, primary language spoken, race/ethnicity, education history, and veteran status.

Primary Safety Endpoint:

Insert Primary Safety Endpoint Statistical Analysis

Insert Primary Safety Endpoint Statistical Table

Primary Effectiveness Endpoint:

Insert Primary Effectiveness Endpoint Statistical Analysis

Insert Primary Effectiveness Endpoint Statistical Table- 8 weeks

Secondary Effectiveness Endpoint:

Insert Primary Effectiveness Endpoint Statistical Analysis

Insert Primary Effectiveness Endpoint Statistical Table: 4, 8, 12 weeks

Sub-Analyses:

Insert Sub-Analyses Statistical Analysis

Insert Sub-Analyses Statistical Tables

Special Controls:

Insert Special Control Section Here

Benefit/Risk Determination:

Insert Benefit/Risk Section Here

Section 5.0: Administrative Information

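### As a plain mean, weeks to initial benefit uses only patients who benefit, so onset looks quick and the figure responds weakly to how many benefit

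*Protocol*

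**What the plan says.** Protocol section 8.3 lists "the mean number of weeks to initial benefit from Nu-V3 device use" among the sub-analyses. The SAP's sub-analyses item repeats it: "study sub-analyses included the mean number of weeks to initial benefit from Nu-V3 device use". Where the SAP's Results section should give the method, it has only a placeholder, "Insert Sub-Analyses Statistical Analysis".

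Neither document defines initial benefit, names the analysis set, or says how a patient without benefit enters the mean. Neither lists the proportion who benefit beside this figure. The only imputation statement in the SAP concerns the primary safety endpoint. For a time-to-event measure, the SAP's own outcome checklist (Section 3.0) asks for a stopping rule and the longest observation time. Neither is supplied here, and Section 3.0 has no template for this outcome.

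Patients without an event are foreseen. Protocol section 4.2 provides for "A lack of significant improvement by the end of week 4", and the SAP's Accountability section tabulates exits before 8 weeks.

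Patients are "treated with the Nu-V3 device for 8 weeks, then observed for an additional 4 weeks" (protocol section 4.0). Under section 4.1, "Evaluations are completed weekly, every 7 days", which gives seven on-treatment checks after baseline (Weeks 2 to 8).

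**The concern.** A patient with no benefit by the last check, or who leaves first, has no week of onset to average. Unless a rule brings such patients in, the mean is conditional on success. It then describes how quickly the successes came and says little about how many there were.

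The SAP presents the study as the pivotal support for a De Novo request, and protocol section 1.1 suggests that relief may be immediate. With a single arm, no control group would put an onset figure in context. An onset of under four weeks could therefore be quoted when most patients never benefited.

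**Working it through.** The documents give no benefit rate, expected onset time or other figure for this endpoint, so there is nothing to reproduce. What follows is an illustration; the rates are assumptions.

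**Inputs**
- K = 7 on-treatment checks after baseline (protocol section 4.1). Time is counted in weeks from baseline, so the Week 8 check is week 7.
- p = chance of first benefit at each check, assumed constant at 5%, 10% or 20%.
- No dropout.

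**Formulas**
- Share who ever benefit: P = 1 − (1 − p)^K.
- Restricted mean in all patients, with non-benefiters counted to week K: R = P / p.
- Mean among benefiters: M = [R − K(1 − P)] / P.
- Median on the weekly grid: the smallest k with 1 − (1 − p)^k ≥ 0.5.

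**Numbers put in**
- p = 5%: P = 1 − 0.95^7 = 0.302; R = 0.302/0.05 = 6.03; M = (6.03 − 7 × 0.698)/0.302 = 3.80.
- p = 10%: P = 1 − 0.90^7 = 0.522; R = 0.522/0.10 = 5.22; M = (5.22 − 7 × 0.478)/0.522 = 3.58.
- p = 20%: P = 1 − 0.80^7 = 0.790; R = 0.790/0.20 = 3.95; M = (3.95 − 7 × 0.210)/0.790 = 3.14.

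(Results are from unrounded values.)

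| p per week | Ever benefit | Mean, benefiters only | Restricted mean, all | Median, all |
|---|---|---|---|---|
| 5% | 30% | 3.8 | 6.0 | 14 (not reached on treatment) |
| 10% | 52% | 3.6 | 5.2 | 7 |
| 20% | 79% | 3.1 | 4.0 | 4 |

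**How far each summary follows the benefit rate.** Fix P and set p = 1 − (1 − P)^(1/7):

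| Ever benefit | Mean, benefiters only | Restricted mean, all |
|---|---|---|
| 90% | 2.8 | 3.2 |
| 50% | 3.6 | 5.3 |
| 20% | 3.9 | 6.4 |
| 10% | 3.9 | 6.7 |

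From 90% to 10% the benefiters-only mean moves 1.2 weeks (2.79 to 3.94), of which only 0.3 week comes after P falls below 50%. Under a constant weekly chance it cannot exceed about 4.0, the midpoint of checks 1 to 7. The all-patient mean moves 3.5 weeks (3.21 to 6.69).

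**Other assumptions**
- If benefiters' timing is fixed (weekly chance 0.4, truncated at 7) and everyone else never benefits, the benefiters-only mean is 2.3 weeks at every P. The restricted mean is 2.8, 4.7 and 6.5 at 90%, 50% and 10%.
- With a constant weekly chance and 8 checks, the benefiters-only mean runs from 3.1 to 4.4 as P falls from 90% to 10%. With 11 checks it runs from 4.1 to 5.9. The pattern is the same.

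**Precision.** Of "a total of 50-100 patients at multiple centers will be registered for study participation", a 10% benefit rate would leave the mean resting on 5 to 10 patients, and fewer within a symptom stratum.

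**The case against.** The strongest reply is that the defect is an unwritten method rather than a wrong one. The documents name a mean and leave the method blank; they nowhere say that non-benefiters are dropped. A restricted mean is also a mean number of weeks and would include everyone. The event itself is undefined, and that question comes before the choice of estimator. All of this stands as description. It limits the point to what happens if the plain mean is computed as named, and nothing in either document directs the analyst elsewhere.

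A reader might infer more than the documents support:
- That the mean can be computed only in benefiters. It cannot be said so strongly, since assigning the last check or using a restricted mean would include the rest.
- That the figure flatters the device whatever the response rate. At 90% benefiting, the gap is about 0.4 week.
- That it hardly moves at all. That holds in the fixed-timing case, and roughly below 50% in the constant case, but not over the whole range.
- That the plan itself ends follow-up for onset at Week 8. In section 8.3 the reference to the 8-week intervention belongs to the sustained-response measure, and questionnaires continue to Week 12.
- That this is nearly the only evidence on onset. The secondary endpoints include symptom change at Week 4, and the weekly questionnaires are to be compared with baseline.

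On importance, the objection is also fair: this is a descriptive sub-analysis with no hypothesis test attached.

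**Conclusion.** The point holds in a limited form. Taken as a plain mean, the planned figure reflects benefiters alone, understates time to benefit across the treated group, and is a weak guide to the share who benefit, especially below about half. In the illustration it reads 3.8 weeks when 70% of patients never benefit on treatment, against 6.0 weeks over all patients.

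The size depends on assumed benefit rates, a constant weekly chance, seven checks and no dropout. The direction does not depend on the number of checks or on which of the two timing assumptions is used. The change is worth making because an onset figure could be quoted alone. No primary or secondary endpoint is affected.

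**What to change.** 1. Pre-specify initial benefit for each stratum, from instruments already collected weekly: which instrument, what threshold, and whether it must be confirmed. The PGIC form's rule, "A significant, favorable change is a score of 5-7", is a candidate for the pain stratum. The same note carries a second rule, a 2-point change from the last score, so the SAP should say which applies. The PGIC question refers to a painful condition, so the other strata need their own symptom scale or PTB-7 item 1, which has no threshold yet.
2. Replace the plain mean with a Kaplan-Meier analysis of time to first benefit in all treated patients of each stratum, to the last on-treatment assessment. Censor patients without benefit at their last assessment.
3. Report the cumulative percent with benefit by Weeks 4 and 8 with confidence intervals, the median if reached, and the restricted mean with its horizon stated.
4. Add a sensitivity analysis counting early exits as no benefit through the last on-treatment check. Censoring at exit assumes that leaving is unrelated to benefit. The SAP's exit reasons include voluntary withdrawal and physician decision, so that may fail; if non-benefiters leave, Kaplan-Meier would itself overstate benefit.
5. Show any benefiters-only mean only beside the number benefiting out of the number treated.

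The cost is a short SAP paragraph and a few lines of code, with no new data. The downside for the sponsor is that the reported time to benefit will look longer.
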